#### Secondary Endpoints:

1. Interstitial glucose (IG) levels below target range, measured by unblinded CGM (inpatient and outpatient), defined as both time (in minutes) and mean decremental area over the curve (AOC (0-300 min) in minutes\*mg/dL) during exercise:
  - Below range, as defined by  $IG \leq 70 \text{ mg/dL} (\leq 3.89 \text{ mmol/L})$

- Below range, as defined by IG between 54 to 70 mg/dL (3–3.89 mmol/L)
- Below range, as defined by IG < 54 mg/dL (<3 mmol/L)
- Proportional time (percentage time within hypoglycemia IG  $\leq$  70 mg/dL (3.89 mmol/L) and clinically significant hypoglycemia IG < 54 mg/dL (3mmol/L)).

2. Insulin utilization as reported by subject at baseline, and weeks 4, 8 and 12 in the outpatient setting.
3. Change from Baseline to the end of the Outpatient Phase in PROs: Barriers to Physical Activity in Diabetes (Type 1) (BAPAD-1), Hypoglycemia Fear Survey (HFS-II), and Hypoglycemic Confidence Scale (HCS).

**Other Secondary Endpoints:**

Change from Baseline in insulin utilization as reported by the subject at Weeks 4, 8, and 12 in the Outpatient Phase.

**Exploratory Endpoints:**

1. Mean time and mean proportional time (%) within range, as defined by IG between 70 and 180 mg/dL (3.89 to 10 mmol/L) (CGM, 0 to 300 minutes with exercise), across the 2 CRC treatment arms.
2. Time, proportional time (percentage), and mean incremental Area Under Curve, plasma glucose  $>$  180 mg/dL (10 mmol/L), and (AUC (0-300 min) in minutes\*mg/dL) during exercise, across the 2 CRC treatment arms and the 3 outpatient treatment arms.
3. The time, proportional time (percentage), and mean incremental area under the curve (AUC) during which plasma glucose  $>$ 250 mg/dL (AUC (0-300 min) in minutes\*mg/dL) during exercise, across the 2 CRC treatment arms and the 3 outpatient treatment arms.
4. Incidence of overnight hypoglycemia as measured by CGM, across the 2 CRC treatment arms and the 3 outpatient treatment arms.
5. Compare the glucose tablet utilization during exercise, across the 2 CRC treatment arms and the 3 outpatient treatment arms.

6. Compare food (carbohydrate) intake pre/post exercise, across the 3 outpatient treatment arms.
7. Compare number of exercise sessions performed across the 3 outpatient treatment arms.
  - a. Conduct subgroup analysis for:
    - i. comparison of the number of qualified exercise sessions out of total number of exercise sessions conducted
    - ii. comparison of the number of qualified sessions meeting less than 30% proportional time at target HR
    - iii. comparison of the number of qualified sessions meeting greater than or equal to 30% proportional time at target HR
8. Compare number of minutes of exercise performed per week, across the 3 outpatient treatment arms.
9. Compare caloric expenditure during exercise, across 3 treatment arms.
10. The change from Baseline to end of study in body weight will be measured and analyzed across the 3 treatment arms.
11. Compare number of steps taken, and the distance achieved during exercise sessions across the 3 outpatient treatments arms.
12. The following assessments during exercise sessions will be captured from the wearable activity monitor: heart rate, daily steps, calories burned, distance covered, floors climbed, active minutes.
13. Change from baseline in HbA1c.

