## Exploratory Objectives

1. To evaluate the glycemic time in range associated with exercise sessions and post exercise.
2. To evaluate the impact of Glucagon RTU (Glucagon Injection) on the quantity of glucose tabs used over time during exercise sessions.
3. To evaluate weight loss or weight maintenance over time.
4. To examine food intake both before and after exercise.
5. To examine the effect of exercise and Glucagon RTU on overnight hypoglycemia following episodes of exercise.
6. To evaluate the effects of exercise and Glucagon RTU use upon changes in hemoglobin A1c.
7. To evaluate the intensity and duration of the frequent exercise sessions.
8. To evaluate overall frequency of aerobic exercise over study period.
9. To evaluate effects on exercise duration and intensity as well as daily activity metrics.

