### 1.3 DETERMINATION OF SAMPLE SIZE

The primary endpoint of the study is the incidence of hypoglycemia (glucose  $\leq$  70 mg/dL (3.89 mmol/L)) associated with an exercise session, which occurred within the 12-week outpatient follow-up, as measured by BGM. The null hypothesis is that there is no difference between the treatment groups in the incidence of exercise-associated hypoglycemia, and the alternative is there is a difference between the treatment groups in terms of the incidence of exercise-associated hypoglycemia. With an effect size estimate of 0.262 (variance of means 59, common standard deviation 15), 80% power and an alpha of 0.05, using a one-way analysis of variance, 14 subjects per treatment group in the Outpatient Stage is required. Accounting for 15% attrition, a total of 48 subjects will be randomized.

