## **2.2 Handling of Missing Data:**

Imputation of missing data will not be performed.

To handle missing or partial AE and concomitant medication dates, the following rules will be applied.

For partial start dates:

1. If the year is unknown, then do not impute the date but assign a missing value.
2. If the month is unknown, then assign “January.”
3. If the day is unknown, then assign “01.”

For partial end dates:

4. If the year is unknown, then do not impute the date but assign a missing value.
5. If the month is unknown, then assign “December.”
6. If the day is unknown, then assign the last day of the month.

After implementing the rules above, to determine whether AEs (or medications) with missing start or stop dates are pretreatment or on/after treatment, the following strategy will be used:

1. If the start date and stop date are both missing, then the most conservative approach is taken and the AE (or medication) is considered to be treatment emergent (or concomitant medication).

2. If the start date is missing but the stop date is not missing and is on or after the day of study dose administration, then the most conservative approach is taken and the AE (or medication) is considered to be treatment emergent (or concomitant medication).
3. If the start date is missing but the stop date is not missing and is before the day of study dose and after the date of signed informed consent, then the AE (or medication) is considered to be before treatment (or prior medication).
4. If the start date is not missing but the stop date is missing, then the most conservative approach is taken, and medication is considered to be concomitant while the AE is defined by start date.

If the Adverse Event Relationship flag is missing, the relationship for adverse event will be defined as related. If the Adverse Event Severity flag is missing, the severity for adverse event will be defined as severe.

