## 4. STATISTICAL METHODOLOGY

### 4.1 Definition of Analysis Population

**All Screened Subjects:** All Screened subjects will include any subject who signed the informed consent form.

**Intention to Treat (ITT) Population:** All randomized subjects regardless of whether they received Study Drug.

**Per Protocol (PP) Population:** ITT participants who completed a qualified exercise session, and who was dosed within the study window and did not meet any of the key exclusion criteria at screening. The definition of qualified exercise is defined in Section 2.4.

**Safety Population:** All randomized subjects who received any amount of Study Drug.

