#### **4.3.8 Exploratory Analysis:**

Glucose levels within range, >180 mg/dl, >250 mg/dl will be measured and analyzed as the mean incremental area under the curve (AUC(0-5hrs) in minutes\*mg/dL) during exercise.

Time and Proportional time (percentage within range, >180 mg/dl, >250 mg/dl) will be calculated and treatment difference will be calculated using ANOVA/Kruskal–Wallis test, based on whether the data is normally distributed or not respectively.

Generally, unless otherwise stated, the mean incidence rates will be compared using the T tests/ ANOVA or ANCOVA models using treatment arm at Outpatient phase, treatment sequence, obtained by combining the received treatments at CRC and Outpatient phase, sex as factors with, if applicable, age and weight as covariates.

Glucose tablet utilization during exercise, food (carbohydrate) intake pre/post exercise, number of exercise sessions completed across the 3 outpatient treatment arms , number of minutes exercised per week, number of calories burned per exercise sessions, number of steps, distance

covered, heart rate, floors climbed and change from Baseline in body weight will be compared for the treatment arms using T tests/ ANOVA at CRC/ Outpatient phase.

Incidence of overnight hypoglycemia will be compared for the treatment arms using Chi-Square/Fisher's exact tests at CRC/ Outpatient phase.

HbA1c data will be summarized using descriptive statistics (n, mean, SD, median, min, and max) for each scheduled study assessment, as well as change from baseline, will be summarized using ITT and PP Population.

Example of SAS syntax code that can be used for exploratory analysis is provided in APPENDIX 3.

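### Outpatient exercise sessions are compared as a count with no allowance for time on study, although the objective is exercise frequency

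*SAP*

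**What the plan says.** The exploratory objective in SAP 1.1 is "To evaluate overall frequency of aerobic exercise over study period". The matching endpoint, SAP section 3 item 7, is "Compare number of exercise sessions performed across the 3 outpatient treatment arms", and sub-items 7a(ii) and 7a(iii) are again numbers of sessions, split by proportion of time at target heart rate. SAP 4.3.8 lists "number of exercise sessions completed across the 3 outpatient treatment arms" among variables that "will be compared for the treatment arms using T tests/ ANOVA at CRC/ Outpatient phase". Protocol 5.2.3 also gives the endpoint as a number with no time unit.

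The next item is scaled for time: "Compare number of minutes of exercise performed per week, across the 3 outpatient treatment arms".

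Three other provisions decide what happens to a subject who leaves early:

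- SAP 2.2: "Imputation of missing data will not be performed".
- SAP 4.1 defines ITT as "All randomized subjects regardless of whether they received Study Drug". The per-protocol set asks for a completed qualified session, not for completion of the 12 weeks. The session tables in SAP 5.1 are run on both sets.
- SAP 1.3: "Accounting for 15% attrition, a total of 48 subjects will be randomized".

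**The concern.** Frequency is sessions per unit of time. A subject who withdraws at week 3 of 12 contributes about 3/12, a quarter, of the sessions of an equally active completer. The planned comparison reads that as less exercise. No offset, exposure term or completer rule corrects for it. The covariates that SAP 4.3.8 allows are treatment sequence, sex, age and weight, not time on study.

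Two things are at stake. Unequal follow-up adds variance and hides a real difference in frequency, even when withdrawal is balanced. If withdrawal is materially unbalanced, arms with the same weekly frequency will show different mean counts. One arm is open-label with no basal reduction, so balance cannot simply be assumed, although nothing in the documents shows imbalance either.

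**Working it through.** **Inputs from the documents.** Outpatient stage 12 weeks (SAP 1.2). Requested frequency 2 to 3 sessions per week, midpoint μ = 2.5 (Protocol 8.4). 48 randomized 1:1:1, so 16 per arm (SAP 1.3, Protocol 8.5). Attrition 15% (SAP 1.3). Two-sided 0.05 (SAP 4.3.6).

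**Assumptions, not in the documents.** Between-subject SD of the weekly rate σ = 0.4 to 1.25. One arm at 3.2 sessions per week against 2.5 in the others. Withdrawal times uniform over weeks 1–12 and unrelated to a subject's own rate. The attrition splits by arm shown below.

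**1. The plan's own figure.** This is for the primary endpoint only; none is given for sessions. f² = 59/15² = 0.262. With 3 × 14 = 42 subjects, λ = 42 × 0.2622 = 11.0 and one-way ANOVA power is 82.3%; with 13 per arm it is 79.0%. So 14 per arm reproduces. For attrition, 42 × 1.15 = 48.3 and 42/0.85 = 49.4, against 48 stated.

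**2. Effect on the mean count.** A withdrawal lasts on average (1 + 12)/2 = 6.5 weeks and loses 5.5 weeks, or 5.5 × 2.5 = 13.75 sessions. With withdrawal proportion p, the mean count is 30 − 13.75p. At p = 0.15 it is 27.9. Each 10-point difference in withdrawal between arms gives a false difference of about 1.4 sessions. At 25/15/5% the arm means are 26.6, 27.9 and 29.3 with the weekly rate at 2.5 throughout.

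**3. Effect on the variance (T = weeks on study, p = 0.15).**

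- E[T] = 0.85 × 12 + 0.15 × 6.5 = 11.175
- E[T²] = 0.85 × 144 + 0.15 × 52.33 = 130.25
- Var(T) = 130.25 − 11.175² = 5.37
- E[1/T] = 0.85/12 + 0.15 × ln(12)/11 = 0.105

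Var(total) = μE[T] + σ²E[T²] + μ²Var(T). At σ = 0.6 this is 27.9 + 46.9 + 33.6 = 108.4, so SD 10.4 and CV 10.4/27.9 = 0.37.

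Var(rate) = σ² + μE[1/T] = 0.36 + 0.26 = 0.62, so SD 0.79 and CV 0.79/2.5 = 0.315.

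The squared CV of the total is about 1.4 times that of the rate. The term μ²Var(T) = 33.6 arises only from differing follow-up.

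**4. Power.** 20,000 simulated trials per case, Poisson counts with gamma-distributed subject rates, one-way ANOVA over three arms, equal attrition:

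| Outpatient attrition | SD per week | Totals | Rate |
|---|---|---|---|
| 15% | 0.4 | 61% | 85% |
| 15% | 0.6 | 52% | 69% |
| 15% | 1.0 | 33% | 39% |
| 15% | 1.25 | 25% | 30% |
| 8% | 0.6 | 60% | 71% |

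With no attrition the two analyses coincide.

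**5. False positives with identical weekly rates, over the same range of SD.**

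| Attrition by arm | Totals | Rate |
|---|---|---|
| Equal, 15% | about 5% | about 5% |
| 20/15/10% | about 5–6% | about 5% |
| 25/15/5% | 7–10% | about 5% |
| 30/10/5% | 8–15% | about 5% |

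**The case against.** The strongest reply is that nothing rests on this test. Item 7 is one of 13 exploratory endpoints, the trial was sized only for the primary endpoint, and power or error rates for session counts were never promised. That stands, and it fixes the grade as minor.

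A total can also be a legitimate target: counting no further sessions after withdrawal is coherent, and a rate while participating can hide that a burdensome regimen drove people out. But the SAP names no such target, and its objective is frequency. What stands is that totals must be shown beside the rate.

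The SAP does not state outright that the variable is an unscaled 12-week total, and it refers to mock tables that are not in the documents. Still, its text gives no denominator here while giving one for minutes. Minutes per week, the qualified proportion in 7a(i) and the disposition tables help a reader notice unequal attrition, but none of them is a session rate.

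Three stronger readings are tempting and not supported:

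- That all 15% is lost in the outpatient weeks. Randomization is at Visit 3, so part may fall in the CRC phase, and SAP 4.3.1 refers to an ITT set for the outpatient phase.
- That the false-positive rate is raised in any case. It is about 5% with equal attrition and barely moves with mild imbalance.
- That the efficacy result is compromised. The primary endpoint relates hypoglycemic events to sessions, and no conclusion about it depends on item 7.

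**Conclusion.** The concern holds as a minor point. As written, SAP section 3 item 7 (with 7a(ii) and 7a(iii)) and SAP 4.3.8 answer a frequency question with a count that also reflects how long each subject stayed. The consequence is extra variance at any level of withdrawal, and a spurious difference only if withdrawal differs materially by arm.

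The loss of power runs from about 24 percentage points when subjects exercise at similar rates to about 5 when they vary widely, and shrinks with lower outpatient attrition. At the wider SDs both analyses are underpowered. All these figures depend on the assumed SD, effect and withdrawal pattern.

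**What to change.** In SAP section 3 item 7 and SAP 4.3.8:

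- Analyze session counts with a negative binomial (or overdispersed Poisson) model, treatment arm as factor and log(weeks in the outpatient treatment phase) as offset. ANOVA on sessions per week is a simpler alternative, but unweighted it gives full weight to noisy rates from very short follow-up.
- Define time at risk: from the start of the outpatient phase (dispensing at the end of Visit 4) to the earlier of the end of the 12-week phase or the withdrawal date. Exclude the 14–21 days to Visit 11, which follow the last exercise session.
- Include subjects who entered the outpatient phase; those who never did have no time at risk.
- Apply the same rule to 7a(ii) and 7a(iii), and use the same weeks for item 8, whose weekly denominator is also undefined.
- Report raw totals, weeks on study and discontinuations by arm descriptively.

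The cost is one derived variable from dispensing and disposition dates that the study already needs. The small downside is that the rate describes frequency while participating, which is why totals and discontinuations must stand beside it.

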**Safety Variables:**

- AEs, SAEs (incidence, frequency, severity), and AEs leading to discontinuation.
- Vital signs (heart rate, blood pressure, respiration rate, temperature).

- 12-Lead ECG.
- Clinical laboratory tests (clinical chemistry, hematology, urinalysis).
- Physical examination findings.
- Draize Scales, Injection Site Discomfort and Duration Questionnaires.

## 4. STATISTICAL METHODOLOGY

### 4.1 Definition of Analysis Population

**All Screened Subjects:** All Screened subjects will include any subject who signed the informed consent form.

**Intention to Treat (ITT) Population:** All randomized subjects regardless of whether they received Study Drug.

**Per Protocol (PP) Population:** ITT participants who completed a qualified exercise session, and who was dosed within the study window and did not meet any of the key exclusion criteria at screening. The definition of qualified exercise is defined in Section 2.4.

**Safety Population:** All randomized subjects who received any amount of Study Drug.

### 4.2 Coding Dictionaries Used

Adverse events and Medical history will be coded using Medical Dictionary for Regulatory Activities (MedDRA) version 22.1.

Prior & concomitant medication will be coded using World Health Organization-Drug Reference List (WHO-DRL) (Version WHODD-B3-MAR 2019).

### 4.3 Wearable Monitoring Devices

There are three wearable devices used for collection and analysis of metrics related to the study endpoints. Each subject has data collected from a wearable fitness tracker (Fitbit Ionic), continuous glucose meter (CGM), and a blood glucose meter (BGM). Endpoint Analysis will require confluence of data from these sources and therefore understanding of each is imperative.

#### 4.3.1 Fitbit® Ionic

The Fitbit is used to collect exercise session metrics, daily activity metrics, and a daily food log. Data collected from this source is based on the reporting capabilities of the online portal fitabase. The Sponsor Study Specific Procedure-002 defines the process for collecting reports from the fitabase source. The metrics collected for analysis are as follows:

- The Activity Log report is collected to capture Date, Start Time, Duration (in milliseconds), Steps, Distance (in kilometres), Elevation Gain (in meters), Calories (in kilocalories), Average Heart Rate (beats per minute), and Active Minutes (in minutes) for each tracked exercise session. Active Minutes are separated into three categories titled Lightly Active, Fairly Active, and Very Active. Specific details for collection and data entry related to the Activity Log report are summarized in the 4-Sep-2019 Xeris Memorandum titled 'Fitbit Data Entry Clarification'.
- The Food Log report is collected to capture Date and the Nutritional Value of the food item in Grams of Carbohydrates. Specific Time of food consumption is not tracked. For analysis, cumulative carbohydrate intake will be summarized each day of a qualified session and compared across the treatment arms.
- The Heart Rate report is collected to capture Date, Time, and Heart Rate Value. Instances of heart rate are collected every minute and will be used to determine qualified exercise sessions.

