5.1.3. Exploratory Objectives

- To evaluate the glycemic time in range associated with exercise sessions and post-exercise
- To evaluate the impact of Glucagon RTU (Glucagon Injection) on the quantity of glucose tabs used over time during exercise sessions
- To evaluate weight loss or weight maintenance over time
- To examine food intake both before and after exercise
- To examine the effects of exercise and Glucagon RTU on overnight hypoglycemia following episodes of exercise
- To evaluate the effects of exercise and Glucagon RTU use upon changes in hemoglobin A1c
- To evaluate the intensity and duration of the frequent exercise sessions
- To evaluate overall frequency of aerobic exercise over the study period

- To evaluate effects on exercise duration and intensity as well as daily activity metrics

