5.2.3. Other Secondary Endpoints

- Change from Baseline in insulin utilization as reported by the subject at Weeks 4, 8, and 12 in the Outpatient Phase.
- Exploratory EndpointsMean time and mean proportional time (%) within range, as defined by plasma glucose between 70 and 180 mg/dL (3.89 to 10 mmol/L) (CGM, 0 to 300 minutes with exercise)
- The time, proportional time (percentage), and mean incremental area under the curve (AUC) during which plasma glucose $>$ 180 mg/dL (10 mmol/L), and (AUC_(0- 300 min) in minutes*mg/dL) during exercise.

- The time, proportional time (percentage), and mean incremental area under the curve (AUC) during which plasma glucose >250 mg/dL (AUC(0- 5 hours) in minutes*mg/dL) during exercise.
- Incidence of overnight hypoglycemia as measured by CGM.
- Compare the glucose tablet utilization during exercise, across the 3 treatment arms.
- Compare food (carbohydrate) intake pre/post exercise across the 3 treatment arms.
- Compare the number of exercise sessions performed across the 3 treatment arms.
- Compare the number of minutes of exercise performed per week.
- Compare caloric expenditure during exercise, across 3 treatment arms.
- The change from Baseline in body weight will be measured and analyzed across the 3 treatment arms.
- Compare the number of steps taken and the distance achieved during exercise sessions across 3 treatments..
- The following assessments during exercise sessions will be captured from the wearable activity monitor: heart rate, daily steps, calories burned, distance covered, floors climbed, active minutes.
- Change from baseline in HbA1c

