10.4. Visit 5 Through 10 – Outpatient Stage

10.4.1. Visits 5 Through 10 – Treatment Day 4-113

During the outpatient stage, subjects will return for clinic visits every two weeks. Activities to be performed at these visits are outlined in the Schedule of Activities ([Table 1](#)[bookmark7](#)).

In the outpatient setting, subjects will perform moderate to high intensity aerobic exercise with a target of at least 2-3 qualifying sessions per week. To be eligible for study drug dosing, the planned aerobic exercise will be 30-75 minutes in duration. Additionally, the subject's BGM must range between 100-180 mg/dL (5.56 – 10 mmol/L) before the exercise session. Subjects must record their carbohydrate intake (eg, both dextrose tabs and carbohydrates from food) 15 minutes before exercise, during the exercise session, and up to 5 hours post-exercise session.

During the exercise session, the subject is to only drink carbohydrate free liquids (e.g., Powerade Zero or comparable product) and will be provided with glucose tabs to use as needed. The subject will take 5 BGM measurements with exercise: at -15 minutes and just before exercise to establish baseline value, at 30 minutes into the exercise session, at the end of the exercise session, and at 30 minutes after the exercise session. There is a ± 2 minute window on all of these time points.

Per ADA guidelines, if a subject's glucose falls to ≤ 70 mg/dL (3.89 mmol/L) during any exercise session, then the exercise session should be stopped, and no more exercise should be completed that same day; the subject should rest, and glucose tabs should be taken every 15 minutes until the hypoglycemia is corrected and euglycemia (confirmed by BGM) is maintained. Subjects will be provided with a supply of glucose tabs and instructed to use these rather than other sources of carbohydrate to treat hypoglycemia.

During the outpatient phase the subject will be provided with the following items for recording study data and will be provided with instructions for use and uploading data to the cloud if applicable.

1. Blood Glucose Meter: Bayer[®] Contour Next One
 - a. Used to collect blood glucose values during exercise sessions and to confirm blood glucose if a value ≤ 70 mg/dL (3.89 mmol/L) is indicated by CGM.
2. Dexcom[®] G5 Continuous Glucose Meter
 - a. Used to collect interstitial glucose measurements on a continuous basis.
3. Fitbit[®] Ionic

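### The exploratory endpoint on food carbohydrate before and after exercise cannot be produced from the untimed daily food log the SAP specifies, and the SAP declares no change

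*SAP*

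**What the plan says.** The objective in Protocol 5.1.3 is "To examine food intake both before and after exercise". The endpoint, in the exploratory list that runs on from Protocol 5.2.3, is "Compare food (carbohydrate) intake pre/post exercise across the 3 treatment arms". SAP section 3 keeps it as exploratory endpoint 6: "Compare food (carbohydrate) intake pre/post exercise, across the 3 outpatient treatment arms". SAP 4.3.8 uses the same pre/post label when it assigns t tests or ANOVA.

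For collection, Protocol 10.4.1 states: "Subjects must record their carbohydrate intake (eg, both dextrose tabs and carbohydrates from food) 15 minutes before exercise, during the exercise session", and then "up to 5 hours post-exercise session". The same section names one instrument for food, the Fitbit food log. The paper diary items it lists are the exercise description with start and stop times, tablet and emergency-kit use, and study drug administration. Food carbohydrate is not among them.

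For analysis, SAP 4.3.1 (Fitbit Ionic) says the food log yields a date and grams of carbohydrate, and adds: "Specific Time of food consumption is not tracked". Its analysis variable is the sum over each day on which a qualified session took place, compared between arms. SAP 4.4, Changes from Protocol, reads NA.

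**The concern.** The endpoint's name asks how much subjects ate before and after exercise. The variable the SAP defines is how much they ate on the day. A programmer who follows the SAP exactly will produce the second quantity to fill a slot labelled as the first. The SAP's introduction gives it precedence over the protocol, so the daily total replaces the windowed measure without the change being listed anywhere.

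What is at stake is the reading of one exploratory result. The protocol's rationale (4.1 and 6.2) says extra carbohydrate around exercise works against caloric balance and weight control, and this is the endpoint that looks at food around the session. A difference, or the lack of one, in whole-day intake does not show what happened in the hours around exercise.

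**Working it through.** The documents give no sample size, power or expected value for this endpoint, so there is no planned figure to reproduce. The check compares the window the protocol asks subjects to record with the period the SAP variable covers.

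**Inputs**
- Before exercise: 15 minutes (Protocol 10.4.1), read as a 15-minute window.
- Session length: 30 to 75 minutes; for dosing eligibility, "the planned aerobic exercise will be 30-75 minutes in duration" (Protocol 10.4.1).
- After exercise: up to 5 hours, or 300 minutes (Protocol 10.4.1).
- SAP variable: one calendar day, 1,440 minutes (SAP 4.3.1, Fitbit Ionic).
- Time of exercise: any point in the day (Protocol Appendix 1).

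**Share of the day inside the protocol window**

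Window = 15 + session + 300 minutes.
- 30-minute session: 15 + 30 + 300 = 345; 345 / 1,440 = 24.0%; outside the window, 76.0%.
- 75-minute session: 15 + 75 + 300 = 390; 390 / 1,440 = 27.1%; outside the window, 72.9%.

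If the 15 minutes is read as a time point rather than a window, these become 330 / 1,440 = 22.9% and 375 / 1,440 = 26.0%. The conclusion is the same.

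**Latest start that keeps the 5 hours within the same date**

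Latest start = 1,440 − 300 − session, in minutes after midnight.
- 30-minute session: 1,440 − 300 − 30 = 1,110, which is 18:30.
- 75-minute session: 1,440 − 300 − 75 = 1,065, which is 17:45.

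For later starts, part of the post-exercise period falls on the next date and drops out of that session day's total.

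**Can the split be recovered?** The diary gives session start and stop times, but a food entry with a date and no time cannot be placed before, during or after them. The daily total therefore adds intake from outside the window for every session and loses some intake from inside it for evening sessions. Neither can be corrected from the log as described.

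**The case against.** The best case for the plan has four parts.

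- **The SAP is open about it.** Section 4.3.1 states the limitation and names the variable actually used, and the planned tables are titled by mean carbohydrate intake and by intake according to hypoglycaemic events, without the words pre or post. This stands in part. A reader might infer that a null result will be reported as no difference in pre/post intake; the table titles do not support that as a certainty. But the endpoint list and SAP 4.3.8 still carry the pre/post label, and SAP 4.4 declares nothing.
- **The daily total is useful.** Whole-day carbohydrate on exercise days bears on caloric balance and would pick up compensatory eating beyond 5 hours. This stands. It is a valid comparison under its own name, and it fails only on the pre/post question.
- **Tablets are covered elsewhere.** A reader might infer that avoided tablet servings will be lost in the daily food total. The documents do not support this: tablets are recorded in the diary and a separate log, and tablet use during exercise is exploratory endpoint 5 with its own outpatient tables. The gap concerns food carbohydrate only.
- **It is late to change collection.** The SAP is dated 05 Dec 2019, refers to a September 2019 memorandum on Fitbit data entry, and describes duplicate timestamps found at data review (SAP 4.3.4). Data were already being collected, so new diary fields cannot recover earlier sessions. This stands and limits the first part of the fix.

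The diary form itself is not in the documents. It may already hold window entries for food; the itemised list in Protocol 10.4.1 does not show them, and the SAP does not use them.

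**Conclusion.** The point holds for one exploratory endpoint. The analysis the SAP specifies cannot produce the quantity the endpoint names, because an untimed daily total cannot be divided at the exercise session. On the protocol's own times, 73% to 76% of the period summed lies outside the recording window, and the post-exercise part is cut off at midnight for sessions starting after 18:30 (30 minutes) or 17:45 (75 minutes).

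These are shares of time, not of grams. A reader might take them as the fraction of carbohydrate that is irrelevant, or as the dilution of a treatment effect. The documents give no intake figures or variances, so neither can be derived. A reader might also take the protocol to demand clock times for food; it asks for recording tied to windows around exercise, which is enough to show the mismatch.

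The gap begins in the protocol, which names no instrument for food except the Fitbit log. Primary, secondary and safety analyses are unaffected.

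**What to change.** 1. **Sessions still to be collected.** Add food-carbohydrate fields to the paper diary for the three periods in Protocol 10.4.1 (15 minutes before, during, and up to 5 hours after), and analyse grams per qualified session by window. The diary already holds session start and stop times. The cost is a small diary revision and slightly more recording by subjects, which the protocol already requires of them. If the diary in use already has such entries, the SAP only needs to name them as the source.

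2. **Data held only as daily totals.** Redefine exploratory endpoint 6 in SAP section 3, and the matching text in SAP 4.3.8, as total daily food-log carbohydrate on qualified-session days. List the change in SAP 4.4, and draw no conclusion from it about intake before or after exercise. The cost is SAP wording only, together with giving up the pre/post question for those sessions.

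Keep tablet use as the separate endpoint it already is.
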